## **6.7. Withdrawals or Discontinuation**

### **6.7.1. Lost to Follow-Up Subject**

A subject will be considered “lost to follow-up” and terminated from the study when all of the following criteria have been met.

- Failure to complete 3 consecutive visits without due cause (after 30 days).
- Documentation of three (3) unsuccessful attempts, one of which must be in written communication, by the Investigator or his/her designee to contact the subject or next of kin.
- A letter from the Investigator to Sponsor reporting subject as lost to follow up.

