2.1.2. Handling Missing Data

In order to provide unbiased and informative findings, no replacement of missing values is planned for any parameters.

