2.1.5. Interim Analysis

An interim analysis will be performed after all patients reach the 6-month time point to support the CE-marking application.

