2.2. Sample size calculation

The primary objective is to demonstrate that the safety of M-Trap, as measured by freedom from device- and procedure-related major adverse events (see Primary Endpoint for definition) through 6-months post-implantation, is non-inferior to historical controls. Using a success rate of 90% (freedom from device- and procedure-related major adverse events), a non-inferiority margin of 25%, >85% power, and one-sided alpha=0.05, a sample size of n=20 patients is needed to demonstrate that M-Trap is as safe as current standard-of-care through 6-months post-surgery. Assuming a 10% dropout rate, up to 22 patients will be treated to have 20 evaluable patients.

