2.4.4. Follow-up Patients characteristics

Descriptive statistical data will be used to draw up a recapitulation of patients' follow-up visit characteristics.

The following data will be presented on the as-treated population at 1Month, 3Months, 6Months, 9Months, 12Months, 15Months and 18Months follow-up visits:

- Physical exam: Weight (kg), BMI (kg/m²), Temperature (°C), Blood pressure (Systolic and Diastolic in mmHg), Heart rate (bpm), Specific abdominal examination performed (Yes/No), Presence of nodules or bumps if Yes (Yes/No) and How many nodules or bumps if Yes, Specific gynecologic examination performed (Yes/No), Presence of nodules or bumps in the cul-de-sac if Yes (Yes/No) and How many nodules or bumps in the cul-de-sac if Yes.
- Chemotherapy: Is chemotherapy complete (Yes/No), Number of IDS patients complete chemotherapy by the 3-month visit, Number of PDS patients complete chemotherapy by the 6-month visit, Number of cycles received since last visit, Is this visit the first one since the completion of chemotherapy (Yes/No), The reasons if chemotherapy is not completed
- Biomarker CA-125: CA-125 test performed (Yes/No), CA-125 results (U/mL), Disease progression as defined by CA-125 criteria (Yes/No).
- CT Scan: Abdominal CT Scan obtained, Pelvic CT Scan obtained, Chest CT Scan obtained, Target lesions site, Target Lesion location, Target Lesion Measurement (mm), New Target lesion, Evaluation of Target Lesions after chemotherapy completion, Non-Target Lesion Sites, Non-Target

STATISTICAL ANALYSIS PLAN

lesion location, Measurement of Non-Target lesion if measurable (mm), New Non-Target lesion, Evaluation of Non-Target Lesions after chemotherapy completion, Objective Subject Response.

CT Scan is not performed at 1Month visit.

- Device(s) Removal: Device(s) removal planned during this visit (Yes/No)
- Ultrasound: Abdominal Ultrasound obtained (Yes/No), The reason specification if No
- Medications: Medication(s) change since last visit (Yes/No)
- Adverse Event: New adverse events occur since last visit (Yes/No)

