2.5. Derived Criteria Calculation

If at least one of the items needed to calculate a derived criterion is missing then the corresponding derived criterion will be considered as missing.

- Derived criterion “ITT population” will be defined as follows:

If “Signed Informed Consent” = “Yes” and the date of signature of the consent form is filled and all inclusion/exclusion criteria are compliant and “Can the patient be treated with M-Trap” = “Yes” then “ITT population” = “YES”, else “ITT population” = “NO”.

- Derived criterion “As-Treated population” will be defined as follows:

If the date of signature of the consent form is filled and are compliant with all inclusion/exclusion criteria and “Can the patient be treated with M-Trap” = “Yes” and at least one device successfully implanted then “As-Treated population” = “YES”, else “As-Treated population” = “NO”.

- Derived criterion “Age at Enrollment” will be calculated as follows:

“Age at Enrollment” = “Date of signature of Informed Consent” – “Birth date” in years

- Derived criterion “Duration of patients Follow-up” will be calculated as follows:

“Duration of patients Follow-up” = “Last patient follow-up date” – “Procedure patient date”

If patient procedure date is missing Baseline/Screening date will be used (for ITT population)

- Derived criterion “Duration debulking surgery” will be calculated as follows:

“Duration debulking surgery” = “end time of debulking surgery” – “start time of debulking surgery”

- Derived criterion “Duration of implantation” will be calculated as follows:

“Duration of implantation” = “end time of implantation” – “start time of implantation”

- Derived criterion “Total number of procedures” will be equal to the number of checked boxes for “Extensive upper abdominal” and “Other procedures”.

- Derived criterion “Total number of extensive procedures” will be equal to the number of checked boxes for “Extensive upper abdominal”.

CRO will send to MTrap an Excel file with the list of all other surgical procedures to count their number.

- Derived criterion “Number of extended procedures (Patankar definition)” will be calculated as follows:

All patients start with a score of 1, since all patients had cytoreduction surgery.

Add 1 to the score if Pelvic or Para-aortic or Inguinal lymph node dissection are ticked or if any other procedure includes lymph node dissection (lymphadenectomy).

STATISTICAL ANALYSIS PLAN

Add 1 to the score if Small bowel resection is ticked.

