Add 1 to the score if Large bowel resection is ticked (colectomy, rectosigmoid resection).

Add 1 to the score if Diaphragm peritonectomy or Full-thickness diaphragm resection (diaphragm resection) is ticked.

Add 1 to the score if Partial hepatectomy (hepatic resection) is ticked.

- Derived criterion “freedom of device- and procedure-related major adverse events through 6 months post-implantation, including shock, cardiac arrest, myocardial infarction, pulmonary embolism, prolonged intubation, unplanned reintubation, or adverse events leading to removal of the device, including infection, seroma formation, mesh migration, bowel obstruction, adhesions, and local cancer progression through the abdominal wall at M-Trap suture sites” which is the primary endpoint will be calculated as follows:

If a MAE occurred in a patient within 6 months \pm 2W post implantation and “Does this event meet the definition of a major adverse event for the primary endpoint?” = “Yes” then “freedom of device- and procedure-related major adverse events through 6-months post-implantation” = “No” else “freedom of device- and procedure-related major adverse events through 6-months post-implantation” = “Yes”.

- Derived criterion “recurrent patients” will be defined as patients with device removal reason “Disease progression as defined by objective RECIST 1.1 and CA-125 criteria” or device removal reason “other” that indicates recurrence. Derived criteria “non-recurrent patients” are the remaining patients. CRO will send to MTrap an excel file with the list of all other reason of device removal to identify the reason that indicates “recurrence”.
- Derived criterion “time to recurrence” will equal to the date of the follow-up visit when “Device removal planned for this visit” is yes minus the procedure date.
- Derived criterion “platinum resistant, recurrent patients” will be defined as “recurrent patients” where the difference between the date of the follow-up visit when “Device removal planned for this visit” is yes and the date of the most recent chemotherapy medication treatment is less than or equal to 180 days.
- CRO will send to MTrap an excel file with the list of the concomitant medication to identify the chemotherapy medication treatment. Derived criterion “platinum sensitive, recurrent patients” will be defined as “recurrent patients” that are not “platinum resistant, recurrent patients”.

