 Table 31: Successful and Unsuccessful implantation on ITT population (Type 6)
 Table 32: Successful and Unsuccessful implantation on AT population (Type 6)

Post-Procedure Ultrasound

Table 33: Abdominal Ultrasound (Type 5)

Device Deficiency

Table 34: Device malfunction occur during the procedure (Type 5)
 Table 35: Device malfunction occur during the procedure description on ITT population (Type 6)
 Table 36: Device malfunction occur during the procedure description on AT population (Type 6)

Follow-up patients Characteristics

Physical Exam

Table 37: Physical Exam by follow-up visit on AT population (Type 3)
 Table 38: Specific Test Performed by follow-up visit on AT population (Type 2)

Chemotherapy

Table 39 : Chemotherapy results by follow-up visit on AT population (Type 4)

Biomarker CA-125

Table 40: Biomarker CA-125 by follow-up visit on AT population (Type 4)

CT Scan

Table 41: CT Scans by follow-up visit on AT population (Type 5)

Target lesions

Table 42: Target Lesions by follow-up visit on AT population (Type5)
 Table 43: Target Lesions Measurements (mm) by follow-up visit on AT population (Type 3)
 Table 44: New Target Lesion by follow-up visit on AT population (Type 2)

	STATISTICAL ANALYSIS PLAN	MTRAP_SAP_v2.0_FINAL redacted.docx MTRAP Page 18/19
--	----------------------------------	--

Table 45: Evaluation of Target Lesions after chemotherapy completion by follow-up visit on AT population (Type 5)

Non-Target lesions

Table 46: Non-Target Lesions by follow-up visit on AT population (Type 5)

Table 47: Non-Target Lesions Measurements (mm) by follow-up visit on AT population (Type 3)

Table 48: New Non-Target Lesion by follow-up visit on AT population (Type 2)

Table 49: Evaluation of Non-Target Lesions after chemotherapy completion by follow-up visit on AT population (Type 5)

Table 50: Objective Subject Response by follow-up visit on AT population (Type 5)

Device removal

Table 51: Device removal during the planned visit by follow-up visit on AT population (Type 5)

Ultrasound

Table 52: Abdominal Ultrasound by follow-up visit on AT population (Type 5)

Medications

Table 53: Medication(s) change since last visit by follow-up visit on As-Treated population (Type 5)

Adverse Events

Table 54: New adverse events occur since last visit by follow-up visit on As-Treated population (Type 5)

Primary Analysis

Primary Safety analysis

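### SAP 2.5 scores every patient without a flagged major adverse event as event-free through 6 months, however short her follow-up; the effect is modest but can only be favourable

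*SAP*

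**What the plan says.** SAP 2.5 derives the primary safety endpoint by a closed two-way rule. A patient with an MAE within 6 months ± 2 weeks of implantation that is flagged as meeting the endpoint definition is No; for all others, "else “freedom of device- and procedure-related major adverse events through 6-months post-implantation” = “Yes". The window limits when the event occurs, not how long the patient must be followed.

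Four other places bear on patients with incomplete follow-up:

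- SAP 2.5 opens with a general rule. "If at least one of the items needed to calculate a derived criterion is missing", the criterion is missing.
- SAP 2.1.2 (and Protocol 10.3) says that "no replacement of missing values is planned for any parameters". Percentages use non-missing observations (SAP 2.1.3).
- SAP 2.2 plans for losses: "Assuming a 10% dropout rate, up to 22 patients will be treated to have 20 evaluable patients". Neither document defines evaluable, and neither analysis set in SAP 2.3.1 requires follow-up.
- SAP 2.4.4 collects a per-visit item, "New adverse events occur since last visit (Yes/No", and SAP 2.5 derives follow-up duration. The endpoint rule mentions neither.

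SAP 2.4.5 names both the ITT and As-Treated populations for the primary safety analysis, but the planned Tables 55 to 57 are As-Treated only.

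**The concern.** Followed as written, the rule credits an event-free patient last seen at week 5 with the remaining time to month 6 as if it had been observed. The same holds for an early death without a flagged MAE. An ITT patient who was not implanted is also scored Yes on an endpoint whose clock starts at implantation. Every such case adds a success, so compared with leaving these patients out or counting them as failures, the freedom rate can only rise.

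This does not fit the rest of the plan. If nobody can become unevaluable through dropout, treating 22 to keep 20 evaluable has no meaning for this endpoint. Filling unobserved time with success is also hard to square with a rule against replacing missing values.

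The 6-month safety analysis supports the CE-marking application (SAP 2.1.5) and the study is not blinded, so the scoring should be settled before the data are seen. Disposition tables, follow-up times and Listing 23 would reveal early leavers but would not say how they should be scored.

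**Working it through.** **Inputs.** From SAP 2.2 and 2.4.5: reference rate 90%, margin 25 points, hence null rate p0 = 0.90 − 0.25 = 0.65; one-sided 5%; 20 evaluable, 22 treated. Assumptions not in the documents: d event-free or partly observed leavers (2 is the planned number; 3 and 4 are shown as a range), and f, the share of a leaver's MAE risk that was observed before she left (0 to 1). The exact binomial test is used; SAP 2.4.5 specifies an exact interval but does not say whether the test is exact.

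**Plan's own figure.** At n = 20 the smallest passing count is 17: P(X ≥ 17 | 20, 0.65) = 0.0444, and power P(X ≥ 17 | 20, 0.90) = 0.867. The stated n = 20 with power above 85% reproduces.

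**Pass limits, exact test against 0.65.**

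| n | Successes needed | MAEs allowed | P at limit | P one lower |
|---|---|---|---|---|
| 22 | 19 | 3 | 0.0245 | 0.0716 |
| 21 | 18 | 3 | 0.0331 | 0.0924 |
| 20 | 17 | 3 | 0.0444 | 0.1182 |
| 19 | 17 | 2 | 0.0170 | 0.0591 |
| 18 | 16 | 2 | 0.0236 | 0.0783 |

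Three MAEs are allowed at n = 20, 21 and 22, so with 2 lost the decision cannot depend on the scoring. At n = 19 or 18 only two are allowed.

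**Same data, two scorings, 3 MAEs, all leavers event-free.**

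| Lost | Literal rule | Leavers not counted |
|---|---|---|
| 2 | 19/22 = 86.4%, p=0.0245, 95% CI 65.1–97.1% | 17/20 = 85.0%, p=0.0444, CI 62.1–96.8% |
| 3 | 19/22, passes | 16/19 = 84.2%, p=0.0591, fails |
| 4 | 19/22, passes | 15/18 = 83.3%, p=0.0783, fails |

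With 2 lost, both pass, but the Clopper-Pearson interval excludes 65% under the literal rule only.

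**Type I error of the literal rule.** P(Bin(22−d, 0.65) + Bin(d, 1 − 0.35f) ≥ 19):

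| d | f = 0 | f = 0.5 | f = 1 |
|---|---|---|---|
| 2 | 0.0444 | 0.0338 | 0.0245 |
| 3 | 0.0591 | 0.0395 | 0.0245 |
| 4 | 0.0783 | 0.0461 | 0.0245 |

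It equals 0.05 at f = 0.217 (d = 3) and f = 0.429 (d = 4).

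**Bias at 65% true freedom, d = 2, f = 0.5.** Literal rule: (20 × 0.65 + 2 × 0.825)/22 = 0.666, or +1.6 points. Leaving out event-free leavers while keeping leavers with an observed MAE as No: expected rate 0.639, or −1.1 points.

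**Power at 90% true freedom (f = 0 / f = 0.5).**

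| d | Literal rule | Event-free leavers excluded |
|---|---|---|
| 2 | 0.867 / 0.848 | 0.867 / 0.848 |
| 3 | 0.885 / 0.857 | 0.705 / 0.703 |
| 4 | 0.902 / 0.867 | 0.734 / 0.681 |

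Missing-as-failure with 2 lost (f = 0): P(Bin(20, 0.9) ≥ 19) = 0.392.

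**The case against.** The SAP's rule is complete as logic: a patient with no event record has no MAE question that could be missing. Where the authors wanted missing-value logic they wrote it out, as for other medical history in the same section. Counting patients with an event over all patients also matches the adverse-event table layout (SAP 5.3.2). This stands. A reader might infer that the documents offer two equal results; they do not. The literal scoring dominates. Reaching the other requires treating the per-visit adverse-event item or follow-up duration as needed under the general missing-item rule, and the endpoint definition names neither.

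Ascertainment is also better than a bare dropout model suggests. Adverse events are recorded before discharge and at 1 month (Protocol 6.2, 6.4). Patients who are still implanted and intend to withdraw have removal and its associated assessments before exit (Protocol 6.7.2). Serious events are reported within 24 hours of awareness (Protocol 8.4). Observing none of a leaver's risk is therefore a worst case.

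A reader might add that the lost-to-follow-up definition, "Failure to complete 3 consecutive visits without due cause", cannot take effect before the analysis, because a patient last seen at 1 month misses her third visit only at month 9. That is true only for late enrollees. "An interim analysis will be performed after all patients reach the 6-month time point", so it waits for the last patient, and enrolment is expected to take nine months (Protocol synopsis).

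Finally, excluding event-free leavers has its own defect: it keeps early leavers with an MAE and drops those without one. The working shows the resulting downward bias and loss of power. None of this justifies scoring unobserved time as observed success.

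**Conclusion.** The point holds as a should-fix. The written rule gives a favourable result to patients whose 6-month status is unknown, and this contradicts the evaluable-patient premise and the no-replacement rule.

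Its size is modest. With 2 lost, the exact decision, type I error and power are unaffected; only the reported rate, p-value and interval change. With 3 or 4 lost and 3 MAEs, the pass or fail decision depends on the scoring.

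A reader might infer that the trial's type I error is inflated. The figures do not support that in general: it exceeds 5% only with at least 3 lost and with less than about 22% (3 lost) or 43% (4 lost) of the leavers' risk observed.

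The number lost beyond 2 and the observed share are assumptions, and the decision results assume the exact test. With an asymptotic z test, 2 lost and 4 MAEs would already divide the scorings (18/22, p=0.049; 16/20, p=0.080).

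**What to change.** In SAP 2.5:

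- Keep No for any patient with a flagged MAE in the window.
- Score an observed Yes only if there is no such event and follow-up reaches at least 6 months minus 2 weeks, using the follow-up duration already derived. Use the same condition to define evaluable in SAP 2.2.
- State before data review which denominator the binomial test uses. Excluding event-free leavers is one defensible choice, but should not be presented as the only correct main analysis.
- Beside the test, report a Kaplan-Meier estimate of 6-month freedom with its confidence interval, censoring event-free leavers at last contact, and a missing-as-failure sensitivity analysis. The latter should stay a sensitivity analysis because of its low power.
- List early deaths with their relatedness, count them as failures in the sensitivity analysis, and state how they enter the Kaplan-Meier estimate.
- State that ITT patients never implanted are not scored on a post-implantation endpoint, and align SAP 2.4.5 with Tables 55 to 57.

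The cost is SAP wording, one estimate and one table, all from data already collected. The endpoint components do not change. The reported freedom rate may be slightly less favourable, and if exclusion is chosen for the test, power falls to about 0.70 with 3 lost.

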### 6.2.3. Device Removal Procedure

Following completion of chemotherapy treatment, M-Trap devices will be removed under one of following scenarios, whichever occurs first:

- (1) In the event of an adverse event necessitating device removal.
- (2) After disease progression as defined by objective RECIST 1.1 and CA-125 criteria. Both criteria must be met as follows:

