#### **7.1.1. Anticipated or Potential Adverse Events**

The list below provides anticipated or potential adverse events that may occur during the study.

Adverse events that may be associated with a general surgical procedure are:

- Allergic reactions or hypersensitivity to medication, including anesthesia
- Anesthesia complications
- Bleeding
- Death
- Deep vein thrombosis
- Delayed or impaired wound healing
- Infection

Adverse events that may be associated with the surgical debulking procedure are: 

- Abdominal collection requiring drainage
- Abscess
- Acute cardiopulmonary failure
- Acute renal failure
- Anastomotic leak or failure
- Anemia
- Bowel / intestinal obstruction
- Cardiac failure / cardiac arrest / myocardial infarction
- Cardiac dysrhythmia
- Cerebrovascular accident
- Coma
- Death
- Deep vein thrombosis
- Diarrhea
- Fever
- Fistula
- Hematoma
- Hemoperitoneum
- Hemorrhage / bleeding
- Hypotension

- Ileus
- Infection
- Nausea
- Pain
- Pancreatitis
- Pancreatic leak
- Perforation
- Pericardial effusion
- Peritonitis
- Pleural effusion
- Pleuresia
- Pneumonia
- Pneumonitis
- Pneumothorax requiring placement of a chest tube
- Prolonged mechanical ventilation
- Prolonged or unplanned reintubation
- Pulmonary embolism
- Renal insufficiency or failure
- Reoperation
- Respiratory complication
- Respiratory distress syndrome
- Sepsis
- Seroma formation
- Shock
- Surgical site infection
- Thromboembolism
- Trauma
- Urethral obstruction
- Vomiting
- Wound dehiscence

Additional adverse events that may be associated with the device removal and cytology/biopsy laparoscopy procedure are:

- Adhesions
- Anesthesia-related complications
- Bruising
- Conversion to laparotomy
- Cyst rupture
- Hematoma
- Incisional hernia
- Injury to blood vessels of the abdominal wall or those of the lower abdomen and pelvic sidewall
- Peritonitis
- Port-site metastases
- Tumor cell peritoneal dissemination (seeding)
- Urinary tract or bowel injury
- Wound infection

Adverse events that may be associated specifically with the M-Trap device are:

- Adhesions
- Bleeding
- Fistula
- Hematoma
- Infection including abscess formation
- Inflammation
- Local cancer progression through the abdominal wall at M-Trap suture sites
- Mesh migration
- Obstruction
- Organ or bowel injury resulting from device removal procedure
- Pain
- Perforation
- Seroma formation

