2.4.5. Primary Analysis

Primary analysis of safety will be performed on the ITT population and the As-Treated populations.

The primary safety endpoint is freedom from device and procedure-related major adverse events through 6-months post-implantation, including shock, cardiac arrest, myocardial infarction, pulmonary embolism, prolonged intubation, unplanned reintubation, or adverse events leading to removal of the device, including infection, seroma formation, mesh migration, bowel obstruction, adhesions, and local cancer progression through the abdominal wall at M-Trap suture sites.

The primary safety endpoint will be analyzed using a unilateral one sample test for binomial proportion at the 5% level. In addition, the exact bilateral 95% confidence interval will also be given. The statistical test for the primary safety endpoint is given by:

- H0: M-Trap freedom MAE incidence \leq 90% - Non-inferiority margin (25%)
- Versus
- HA: M-Trap freedom MAE incidence $>$ 90% - Non-inferiority margin (25%)

A modified primary analysis will also be performed that uses a freedom from MAE incidence rate that is adjusted for the surgical complexity of the study population, as compared to the Patankar study population, which is the basis of the statistical rationale for this study (repeated in the table below). The total number of extended procedures will be split in four classes: 0, 1, 2, 3 and more.

Procedures	0	1	2	3 or more	AVG
Total patients	1352	1214	254	50	2870
Severe complications, n	51	92	44	9	196
Severe complications, %	3.8%	7.6%	17.3%	18.0%	6.8%

A further modified primary analysis will also be performed that only includes procedure-related events through 30 days, as this is the comparable population to the Patankar study population, which is the basis of the statistical rationale for this study.

Primary analysis of performance will be performed on the As-Treated population and by device location. This analysis will be also performed using these 3 following sub-populations: (1) platinum resistant, recurrent patients; (2) platinum sensitive, recurrent patients; (3) non-recurrent patients (see definition in part 2.5).

The primary performance endpoint is histopathologic evidence of tumor cell capture (see 2.5). Histopathology will be performed after device explant.

The primary performance endpoint will be assessed with exact one-sided 90% confidence intervals.

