2.4.7. Device Removal

Descriptive statistical data will be used to draw up a recapitulation of the device removal details at the time of the removal operation.

The following data will be presented on the As-Treated population on patients number:

- Duration until device removal (days), Reason for removal, All devices removed (Yes/No), The number of devices removed if No. Duration until device removal (days) if the reason for removal is recurrence.
- The time to recurrence will be described using a Kaplan Meier curve. Patients lost to follow-up before the removal will be censored at the date of last follow-up. Patients who have removal for another reason than recurrence before the 18 months will be censored at the date of the removal.
- Disease Focalization: Disease focalization score, Modalities used for the assessment of disease focalization, If a peritoneal wash performed, were malignant cells present (Yes/No)
Disease Focalization will be also analyzed using the 3 sub-populations defined below ((1), (2), (3)), and using the populations (1) and (2) combined and overall.
- Adverse Event: New adverse event(s) occur during removal procedure (Yes/No)
- Cytology (Done with final device removal): Where ascites present (Yes/No), Were malignant cells present in the ascites (Yes/No), Was a peritoneal wash performed (Yes/No), From which area was the wash obtained if "Yes", Were malignant cells present in the peritoneal wash.

	STATISTICAL ANALYSIS PLAN	MTRAP_SAP_v2.0_FINAL redacted.docx
		MTRAP Page 14/15

- Biopsies (Done with final device removal): Biopsy location, Biopsy taken (Yes/No), Is visible tumor present (Yes/No), Is microscopic disease present (Yes/No)

If Biopsy location is Adhesive bands, abnormally scarred areas or Retroperitoneum the further details given will be described by the mean of listing.

The following data will be presented on the As-Treated population on devices number:

- Location of Device, Attachment of the device to the surrounding tissues
- Assessment of device removal: Ease of locating M-Trap device, Did the M-Trap device remain securely fixed in its original location, Ease of removing M-Trap device, Endobag used, Trocar size (mm)
- Core Lab: Device(s) sent to the core laboratory (Yes/No), the Reasons and the Location if No

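### SAP 2.5 reads recurrence off the removal reason and has no rule for a removal recorded as an adverse event when that event is cancer progression at the M-Trap suture sites

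*SAP*

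**What the plan says.** SAP 2.5 derives recurrence from one field. Recurrent patients "will be defined as patients with device removal reason" of progression by RECIST 1.1 and CA-125, or with an 'other' reason that indicates recurrence. The non-recurrent are whoever is left. A review step, meant to pick out recurrences, supports the second route: "CRO will send to MTrap an excel file with the list of all other reason of device removal to identify the reason that indicates".

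Protocol 6.2.3 gives three removal scenarios and applies the first to occur. The first is "In the event of an adverse event necessitating device removal". The second is "After disease progression as defined by objective RECIST 1.1 and CA-125 criteria. Both criteria must be met as follows". The third is the 18-month time point.

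The primary safety definition in SAP 2.4.5, like Protocol 4.1.1, includes "adverse events leading to removal of the device, including infection, seroma formation, mesh migration, bowel obstruction, adhesions, and local cancer progression through the abdominal wall"; the location it gives for that progression is where the device is sutured. Protocol 7.1.1 lists the same event among those specific to the device: "Local cancer progression through the abdominal wall at M-Trap suture sites".

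For the time-to-recurrence curve, SAP 2.4.7 states: "Patients who have removal for another reason than recurrence before the 18 months will be censored at the date of the removal".

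**The concern.** One cancer event can be recorded under two of the protocol's removal scenarios, and the SAP gives it opposite values. Suppose two patients have the same finding, tumour growing through the abdominal wall at a suture site at month 8. One removal is recorded as disease progression: that patient is recurrent and an event on the curve. The other is recorded as an adverse event: that patient is non-recurrent and is censored at removal.

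Three analyses depend on this. Recurrent patients are the denominator of the primary performance endpoint in Protocol 10.3 and of the four focalization percentages in Protocol 10.3 and SAP 2.4.6. They are the parent group of the platinum-resistant and platinum-sensitive subgroups in SAP 2.5. They supply the events for the Kaplan-Meier curve in SAP 2.4.7. Censoring a patient because her cancer progressed is informative, so the curve would understate recurrence. The event that would be lost is progression at the device itself, which is of direct interest in a study of disease focalization.

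**Working it through.** **1. The plan's own figure.** The only sample-size statement (Protocol 10.1, SAP 2.2) concerns safety: n = 20, 90% freedom from major adverse events, margin 25 points (null 65%), one-sided alpha 0.05, power above 85%. Exact binomial:

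- P(X ≥ 16 | 20, 0.65) = 0.118, too large. P(X ≥ 17 | 20, 0.65) = 0.0444, so the test rejects at 17 of 20 or more.
- Power = P(X ≥ 17 | 20, 0.90) = 0.867.

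The figure reproduces. The removal-reason rule does not enter it, so it stands whatever is decided here. The plan states no figure for recurrence or capture.

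**2. The classification, text against text.**

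- The safety definition and Protocol 7.1.1 both treat suture-site progression as an adverse event, and the safety definition places it among those leading to removal. That matches the first removal scenario.
- The second scenario requires both RECIST 1.1 and CA-125. A suture-site tumour can satisfy RECIST as a new lesion. If CA-125 has not met its criterion, the second scenario is not satisfied, and the adverse-event scenario is then the only listed one open before month 18.
- An adverse-event reason is neither the progression reason nor, read strictly, the 'other' reason. The patient therefore falls among the remaining, non-recurrent patients.
- Her removal then counts as one for a reason other than recurrence, and SAP 2.4.7 censors her at that date.

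**3. Illustrative size on the curve.** Assumptions: 22 patients, 10 recurrences by month 12 (45%, within the 40-50% in Protocol 1.5), detected 3 at month 6, 4 at month 9 and 3 at month 12, with no other censoring. Let k of the month-9 recurrences instead be recorded as adverse-event removals at month 8. Recurrence = 1 − ∏(1 − d/n):

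| k | Survival product | 12-month recurrence |
|---|---|---|
| 0 | (19/22)(15/19)(12/15) = 0.545 | 45.5% |
| 1 | (19/22)(15/18)(12/15) = 0.576 | 42.4% |
| 2 | (19/22)(15/17)(12/15) = 0.610 | 39.0% |

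**4. Illustrative size on capture.** Assume 6 of 10 recurrent patients show capture. The exact one-sided 90% lower limit is the 10th percentile of Beta(x, n − x + 1):

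| Recurrent group | Capture | Lower limit |
|---|---|---|
| All 10 classified as recurrent | 6/10 = 60.0% | 35.4% |
| One patient with capture moved out | 5/9 = 55.6% | 30.1% |
| One patient without capture moved out | 6/9 = 66.7% | 40.1% |

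If the moved patient has capture, the non-recurrent group goes, for example, from 2/12 (16.7%) to 3/13 (23.1%). The direction depends on her histology, which cannot be known in advance.

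**The case against.** A reader might infer that every suture-site progression will be misclassified. The documents do not support that. The form's list of removal reasons is not in them; SAP 2.5 names only the progression and 'other' values, and the adverse-event value is inferred from the protocol's first scenario. The safety definition does not say how a removal reason is coded. A patient who meets both RECIST 1.1 and CA-125 may well be recorded as progression. This stands, and it makes the point conditional.

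The sponsor's review of other removal reasons might also catch the case, if that phrase means every reason apart from the progression one. The wording allows this, but it directly follows a sentence about the 'other' category, and the strict reading is the more natural. A prespecified rule should not turn on which reading is taken, particularly in a non-blinded study where the sponsor makes the call.

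The effect is also modest. The curve is descriptive, and the performance intervals have no success threshold. SAP 2.4.5 reports capture on the whole As-Treated population, which is unaffected, and SAP 2.4.6 reports focalization overall as well. A shift of 3.1 points (45.5 − 42.4) is small beside a standard error of about 10.6 points, √(0.545 × 0.455/22). All of this stands, and it limits the weight of the point. It does not supply the missing rule.

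A reader might also assume that the event is at least always counted in the primary safety endpoint. It is not. SAP 2.5 counts events only within 6 months ± 2 weeks, so the month-8 patient would appear only in the adverse-event tables.

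**Conclusion.** The point holds as a conditional gap. If suture-site progression leading to removal is recorded under an adverse-event reason, SAP 2.5 read strictly scores the patient non-recurrent, removes her from the recurrent-patient denominators and platinum subgroups, and SAP 2.4.7 censors her informatively. The documents make that coding likely enough to need a rule, because they themselves name the event as an adverse event leading to removal, but they do not make it certain.

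The size is unknown because no frequency is given. Under the assumptions above, one case moves 12-month recurrence by about 3 points and two cases by about 6.5 (45.5 − 39.0). Capture among recurrent patients may rise or fall, so a claim that the rule flatters the device on capture would not be supported. The primary safety test, its 17-of-20 rejection rule and n = 20 are untouched. The change is worth making before analysis, since with about ten recurrent patients a single classification is visible in the result.

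**What to change.** In SAP 2.5, extend the second route to recurrence: a removal recorded under an adverse-event reason counts as recurrent when that event is local cancer progression, including at the M-Trap suture sites. State that the listing sent to the sponsor for review covers adverse-event removal reasons as well as 'other'.

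Date the event by the rule SAP 2.5 already uses for recurrent patients, the visit at which removal was planned. Using the date when progression was documented would put two clocks on one curve and would not match the platinum-resistant definition, which also runs from the planned-removal visit.

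In SAP 2.4.7, exclude these removals from the censoring rule for reasons other than recurrence. State that the event enters the primary safety endpoint only if it falls within 6 months ± 2 weeks, and that later ones are reported in the adverse-event tables.

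The cost is a few SAP sentences and one programming condition on data already collected. There is a small downside: the recurrence count may be slightly higher, and these patients need not have met both RECIST 1.1 and CA-125, so they should be flagged in the device-removal listing. The change concerns classification in the analysis only and implies nothing about when devices are removed.
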